3 STUDY OBJECTIVES

3.1 Primary Objectives

To assess the anti-neoplastic activity of flotetuzumab in patients with PIF/ER AML, as determined by the proportion of patients who achieve CR/CRh.

3.2 Secondary Objective(s)

Collectively, the secondary objectives of this study are:

- Assessment of CR rate, CRh rate, overall complete response rate (CR, CRh, CRi [CRn, CRp], or MLFS), objective response rate (CR, CRh, CRi [CRn, CRp], MLFS, or PR), time to response and duration of response (DOR).
- To measure early mortality rates, overall survival (OS) and event-free survival (EFS).
- To determine the rate of eligible patients, per institution criteria, that transition to successful stem cell transplant after achieving complete response (CR, CRh, CRi [CRn, CRp], or MLFS).
- To assess rate of conversion to and maintenance of transfusion independence.
- To evaluate duration of initial hospitalization for flotetuzumab administration.
- To evaluate incidence and duration of hospitalizations subsequent to initial discharge.
- To monitor the safety and tolerability of flotetuzumab.
- To characterize the PK and immunogenicity of flotetuzumab.
- To determine safety and efficacy of tocilizumab in the treatment of IRR/CRS.

3.3 Exploratory Objectives

The exploratory objectives of the study are:

- To evaluate CD123 expression on blast cells
- To evaluate circulating cytokine levels at baseline and over time
- To evaluate circulating leukemic and normal cells at baseline and over time
- To evaluate circulating T lymphocyte populations and activation markers at baseline and over time
- To evaluate leukemic cells, leukemic stem cells, normal progenitor cells and T lymphocytes at baseline and over time in the bone marrow
- To evaluate molecular markers of minimal residual disease (MRD)
- To examine changes in T lymphocyte repertoire

- To evaluate the correlation between cytogenetic abnormalities with responses to flotetuzumab immunotherapy.
- To study adaptive immune changes during flotetuzumab treatment.
- To study the tumor microenvironment immune contexture.
- Ruxolitinib Cohort Objectives:
 - To characterize the onset, duration, and severity of IRR/CRS on an exploratory, pilot basis in flotetuzumab-treated patients receiving ruxolitinib and compare that to historical experience in patients not receiving ruxolitinib.
 - To measure and compare cytokine profile and T-lymphocyte populations in patients receiving the combination of ruxolitinib and flotetuzumab vs flotetuzumab alone.
 - To determine the safety and tolerability of the combination of ruxolitinib and flotetuzumab.

4 STUDY DESIGN AND PLAN

4.1 **Overall Study Design and Plan**

This is an open-label, multi-dose, single-arm, multi-center, Phase 1/2, dose-escalation and expansion study. As of Protocol Amendment 11 the trial design was updated to a single arm pivotal study going forward to evaluate efficacy and safety of flotetuzumab for PIF/ER AML patients.

4.2 Sample Size Determination

The planned sample size for the pivotal portion of the study as of Protocol Amendment 11 is 170 patients, based on a three-stage design.

To determine the sample size under inclusion criteria, historical reference response rates to standard treatments were ascertained through a meta-analysis based on 5 published studies that included PIF/ER AML patients selected from 963 publications identified through database search (1; 2; 3; 6; 7). The response rate identified by the meta-analysis is based on a random intercept logistic regression model, yielding a combined CR/CRh rate for PIF/ ER AML of 11.8%, with a 95% confidence interval of 9.4% to 14.7% (Figure 1).

Figure 1 Forest Plot for Meta-analysis

Study	Events	Total		Proportion 95%-CI
1, CLASSIC I (FaderI JCO 2012) 2, VALOR (Ravandi Lancet Oncol 2015), Refractory 3, VALOR (Ravandi Lancet Oncol 2015), Early Relapse 4, Admiral (Gilteritinib), Chemo 5, Anti CD33 ADC Gemtuzumab, Phase I 6, Anti CD33 ADC Gemtuzumab, Phase II 7, Venetoclax w/ HMA,or LDAC(2) MDACC, Di Nardo	15 16 13 2 4 2	83 149 129 124 14 36 43		0.181 [0.105; 0.280] 0.107 [0.063; 0.169] 0.124 [0.073; 0.194] 0.105 [0.057; 0.173] - 0.143 [0.018; 0.428] 0.111 [0.031; 0.261] 0.047 [0.006; 0.158]
Fixed effect model Random effects model Heterogeneity: $I^2 = 0\%$, $\tau^2 = 0$, $p = 0.49$		578	0.1 0.2 0.3 0.4	0.118 [0.094; 0.147] 0.118 [0.094; 0.147]

The result obtained with the Bayesian method is consistent with the result of the random intercept logistic regression model (Table 1).

Assumption	Point Estimate	95% Credible Intervals (Highest Posterior Density)	95% Credible Intervals (Equal-tail)
Normal prior, normal (0, var=10000)	11.7%	(9.3%, 14.7%)	(9.2%, 14.6%)
Beta prior, beta (1, 1)	11.9%	(9.4%, 14.6%)	(9.4%, 14.7%)

Table 1Meta-analysis Using Bayesian Method

The upper 95% CI of 14.7% was chosen as the rate for the null hypothesis (H0) and a target of 23% CR/CRh was established as a clinically meaningful endpoint in this patient population.

A three-stage design with two interim analyses was employed to test the null hypothesis (H0) of CR/CRh rate = 14.7% against the alternative hypothesis (H1) of CR/CRh rate = 23%. Demonstration of CR/CRh rate improvement (H1) by rejecting H0 at a 1-sided type I error of 0.025 with adequate power (80%) in a sequential design requires 170 patients. Specifically, the planned number of patients and the futility and efficacy boundaries at each stage are as follows:

- a. **First interim analysis:** The first interim analysis will be performed after 40 patients have been enrolled and either have had their responses evaluated or were discontinued for any reason from study treatment prior to their first response assessments. This interim analysis is for futility only, that is, the study enrollment will continue if at least 5 (12.5%) out of 40 patients have response of CR/CRh.
- b. Second interim analysis: If the enrollment continues after the first interim analysis, a second interim analysis will be performed after additional 60 patients have been enrolled (100 patients in total) and either have had their response evaluated or were discontinued for any reason from study treatment prior to their first response assessment. This interim analysis is for both futility and efficacy. Specifically,
 - i. If the number of CR/CRh is less than 15 (15%) out of 100 patients, then the study is considered futile and enrollment will be stopped.
 - ii. If the number of CR/CRh is 15 (15%) or greater out of 100 patients, then enrollment will continue.

- iii. If the number of CR/CRh is 25 (25%) or greater out of 100 patients, then H0 is rejected and the study is considered positive. The enrollment will still continue.
- c. **Final analysis:** If enrollment continues after the second interim, then the final analysis will be performed after additional 70 patients have been enrolled (170 patients in total) and either have had their response evaluated or were discontinued for any reason from study treatment prior to their first response assessments. If the number of CR/CRh is at least 35 (20.6%) out of the total of 170 patients, then H0 is rejected and the study is considered positive.

The above design yields a 1-sided alpha of 0.005 for the efficacy boundary at the second interim analysis and an overall 1-sided alpha of 0.024 with approximately 80% power at the final analysis (**Table 2**). The probability of early termination under H0 (futility) in the first two stages is 55%.

CP-MGD006-01: Statistical Analysis Plan

MacroGenics, Inc. Version 3.0, 19 April 2021

Table 2	Three Stage Design
---------	--------------------

H0 (Benchmark CR/CRh rate)	H1 (Target CR/CRh rate)	Stage 1			Stage 2		Efficacy interim analysis at the end of Stage 2		1-Sided alpha for rejecting H0	Power under H1			
14.7%	23%	N1	Move to Stage 2 if # (%) of CR/CRh ≥	N2	N1+N2	Move to Stage 3 if # (%) of CR/CRh ≥	Trial success if # (%) of CR/CRh ≥	1-sided alpha for rejecting H0	N3	Total (N1+N2+N3)	Trial success if # (%) of CR/CRh ≥	0.024	80%
		40	5 (12.5%)	60	100	15 (15.0%)	25 (25.0%)	0.005	70	170	35(20.6%)		

5 STUDY POPULATIONS

Three populations will be used for analysis, the efficacy population, safety population and the evaluable population, as defined below:

- Efficacy population All patients that have been enrolled under protocol amendment 11 or later and treated with flotetuzumab at the MTD of 500 ng/kg/day as a continuous 7-day per week IV infusion during Cycle 1, have received any portion of one dose of flotetuzumab, and met the definition of PIF/ER AML based on Amendment 11 inclusion criteria . This population will be used for the primary analysis of efficacy endpoints.
- Safety population All patients who received any portion of any dose of flotetuzumab. AML and MDS will be analyzed as pooled and separate populations for safety and PK. The analysis of all safety endpoints will be based on the safety population.
- **Response evaluable population** All patients in the efficacy population that have a baseline bone marrow assessment, have at least one post-infusion assessment of their disease status or were removed from the study for reason of documented evidence of disease progression, death, or treatment-related adverse event. This population will be used in the summary of response rate as a secondary analysis.

Patients who die before having a post-infusion disease assessment will be considered evaluable for OS and EFS analyses.

6 STUDY ENDPOINTS

6.1 Primary Efficacy Endpoint

The primary efficacy endpoint for the PIF/ER AML pivotal expansion cohort is the rate of CR/CRh as assessed by the study investigators.

6.2 Secondary Efficacy Endpoints

Key secondary endpoints are listed in Table 3.

Table 3Key Secondary Endpoints

Name	Description
Duration of response (DOR)	Time of initial documentation of response to the time of disease relapse or death due to any cause, whichever occurs first.
Rate of post-baseline transfusion independence	Rate of no transfusion during any consecutive 56-day period on-study.
Rate of HSCT	Rate of successful HSCT through study treatment.
Incidence and duration of hospitalization	Duration of initial hospitalization as well as incidence, number and durations of subsequent hospitalizations following the initial discharge, number of days hospitalized, and reasons for hospitalization.
CR rate	Rate of complete remission.
CRh rate	Rate of complete remission with partial hematologic recovery.

The additional secondary endpoints are listed in Table 4.

Name	Description
Overall complete response rate	Rate of achievement of BM blast of < 5%, CR+CRh+CRi [CRn, CRp]+MLFS according to IWG AML response criteria.
Objective response rate	Rate of CR+CRh+CRi [CRn, CRp]+MLFS+PR according to IWG AML response criteria.
Overall survival (OS)	Time from first dose to death from any cause.
Event-free survival (EFS)	Time from first dose to the date of relapse after CR/CRh/CRi [CRn, CRp], or death from any cause, whichever occurs first.
Time to response (TTR)	Time from first dose to the first CR, CRh, CRi (CRn, CRp), or MLFS.
Mortality rate at 30, 60, 90 and 180 days	Rate of death from any cause within 30, 60, 90, 180 days of first study dose.
Six-month survival rate	Probability of survival at 6 months from first study dose.
One-year survival rate	Probability of survival at 1 year from first study dose.
Immunogenicity	Proportion of patients who become positive for anti-drug antibody production.
Pharmacokinetics	Evaluation of serum concentration of flotetuzumab and its relationships with efficacy, safety and correlative endpoints.

Table 4 Additional Secondary Endpoin	ble 4	Additional Secondary Endpoints
--------------------------------------	-------	--------------------------------

6.3 Safety Endpoint

Safety assessments include evaluation of type, frequency, severity, and relationship to flotetuzumab treatment of AEs, SAEs and AESIs. These events will be recorded by the Investigators in the electronic case report forms (eCRFs). Verbatim terms will be coded to lower-level terms in the Medical Dictionary for Regulatory Activities (MedDRA) and graded by the National Cancer Institute (NCI) Common Terminology Criteria for Adverse Events (CTCAE) version 4.0, except for infusion related reaction/cytokine release syndrome events which are defined by the modified criteria proposed by Lee et al (5). The most current version of MedDRA will be used. Additionally, the safety evaluation includes clinical laboratory evaluations, death, physical examination, vital signs, ECOG performance status, electrocardiogram (ECG) and concomitant medications/surgeries/procedures/therapies.

7 STATISTICAL METHODOLOGY

7.1 General Considerations

Safety and efficacy summaries will be provided for each dose level cohort.

Unless otherwise specified, the following general considerations are applied in data analyses:

- All statistical tests will preserve a significance level of 0.05 for two-sided tests, unless otherwise specified.
- The baseline value is defined as the latest value at the time of or prior to the first dose of study treatment.
- Categorical data will be summarized by the number and percent of patients falling within each category.
- Continuous variables will be summarized by descriptive statistics, including mean, standard deviation, median, minimum, and maximum.
- Time-to-event endpoints will be summarized by the number and percent of the event, median time and corresponding 95% confidence interval (CI), and event free rate and corresponding 95% CI at the specified time points of interest.
- To summarize safety/efficacy data by visit, the post-baseline results will be summarized by the scheduled visit or the derived visit as appropriate.
- In general, the derived visit is the same as the scheduled visit in the protocol which is defined by study day; data that is closest to derived visit (before and after) will be used as the value for that visit. In case that two data collected at the equal distance to the derived visit, the later one will be used.
- Summaries in the Safety Population will be reported by dose cohort and total population; summaries in the Efficacy Population will be reported by PIF, ER and the combined PIF/ER total population.
- The impact of COVID-19 may be assessed and analyzed on a case by case basis. In particular, the following analyses may be performed if there are enough COVID-19 positive patients to render the analyses meaningful:
 - Number of patients discontinued study treatment and/or discontinued from study due to COVID-19, if such reason is collected
 - o Summary of tumor response, PFS and OS
 - Summary of study drug interruption, delay or withdraw due to COVID-19, if such reason is collected
 - Listing of protocol deviation due to COVID-19 separately

• All data summaries and tabulations will be conducted using SAS® software Version 9.3 or higher.

7.2 Missing Data

Data that are reported as missing will be treated as missing in all data summaries. Imputation rules for partially recorded dates, in cases where complete dates were required to carry out an analysis, will be described in the Statistical Programming Plan (SPP). In descriptive summaries for safety, observations that appear spurious (extreme values relative to the majority of the data) will not be altered or removed from the summary.

8 PATIENT DISPOSITION AND BASELINE CHARACTERISTICS

8.1 Patient Disposition

For patient disposition, the number and percentage of patients who reach various study milestones are summarized: All screened patients are broken down by screen failures (with reasons if collected) and enrolled. Then the category of enrolled patients is broken down by "never treated" (with reasons if collected) and "treated". The category of treated patients will further be broken down by "treatment ongoing" and "treatment discontinued" (with reasons for discontinuation, which also include protocol-defined treatment completion, if any).

A summary of patient disposition will be presented for both safety and efficacy population.

8.2 Patient Demographics and Baseline Characteristics

8.2.1 Demographics

Age (year), height (cm), weight (kg), body mass index (kg/m²), and other continuous baseline characteristics will be summarized using descriptive statistics (N, mean, standard deviation, median, minimum, maximum), while age group (< 70 years, \geq 70 years), gender, ethnicity, race, geographic region and other categorical variables will be provided using frequency tabulations (count, percent) for both safety and efficacy population.

Age or year of birth will be recorded on the eCRF. Where age is not recorded, age will be calculated as follows: Age = year of informed consent- year of birth + 1.

Body mass index (BMI) will be calculated as follows: BMI (kg/m^2) = weight in kg/height in m².

8.2.2 Baseline Disease Characteristics

Baseline disease characteristics will be summarized using descriptive statistics.

- 1. Eastern Cooperative Oncology Group (ECOG) performance status;
- 2. Prior AML therapies;
- 3. Primary induction failure (yes versus no);
- 4. Early relapse (yes versus no), if yes, duration of initial CR (CR1);
- 5. Relapse (yes versus no);
- 6. Initial AML subclassification;
- 7. Genetic and cytogenetics abnormalities at baseline;
- 8. Prior chemotherapy/immunotherapy (not related to study indication, for patients with treatment-related secondary AML) (yes versus no);

- 9. Prior radiotherapy therapies (Not Related to Study Indication, for patients with treatment-related secondary AML) (yes versus no);
- 10. Prior surgery/procedure (Not Related to Study Indication) (yes versus no);
- 11. Bone marrow blasts (%) and category (< 20%; 20% to < 30%; 30% to < 50%; \geq 50%) from the screening bone marrow aspirate sample;
- 12. Peripheral blood blast (%);
- 13. Baseline values of the following lab parameters: hemoglobin, platelet count, absolute neutrophil count (ANC), white blood cells (WBC);
- 14. Number of red blood cell (RBC) transfusions and number of units transfused, and number of platelet transfusions and number of units transfused within 28 days prior to first dose;
- 15. The medical and surgical history will be summarized by the Medical Dictionary for Regulatory Activities (MedDRA) latest version by system organ class (SOC) and preferred term (PT).

8.3 **Prior/Concomitant/Follow-up Medications/Procedures/Therapies**

Prior medications/procedures/transfusions are defined as medications/procedures/transfusions that were started prior to first dose or have start dates missing.

Concomitant medications/procedures/transfusions are defined as non-study medications/procedures/transfusions that are started on or after first dose but before EOTV date or started before the start of the study treatment and ended or remain ongoing during the study treatment. Medication/procedure/transfusion with missing start date but end date on or after first dose date and before EOTV date or with both missing start date and end date is also considered as concomitant medication/procedure/transfusion.

Follow-up medications/transfusions are defined as non-study medications/transfusions that are started after EOTV date.

8.3.1 Prior/Concomitant/Follow-up Medications

All prior, concomitant and follow-up medications will be summarized in frequency tabulations (patient counts and percentages) and by World Health Organization ATC first level and PT. All tables described in this section will be produced for both safety and efficacy population.

8.3.2 Prior/Concomitant/Follow-up Surgeries/Procedures

All prior, concomitant and follow-up procedures/surgeries will be summarized in frequency tabulations (patient counts and percentages) and by SOC and PT. All tables described in this section will be produced for both safety and efficacy population.

8.3.3 **Prior/Follow-up Anti-Cancer Therapies**

Anti-cancer therapies include radiotherapy, induction/consolidation/ maintenance/salvage therapies, chemotherapy and immunotherapy. A listing will be provided for anti-cancer therapies.

8.3.4 Prior/Concomitant/Follow-up Transfusions

The number of patients receiving any transfusion product, and the number of patients receiving any transfusion type (red blood cells (PRBCs), whole blood, platelets, plasma, other) will be summarized by dose cohort groups. Prior /concomitant/follow-up transfusions will be summarized in separate tables for both safety and efficacy population.

Transfusion type, number of units, reasons for taking transfusion, and dates of transfusions will be listed in a listing.

9 STUDY DRUG EXPOSURES

All analyses of treatment exposure will be conducted using the safety and efficacy population.

The summary of study drug exposure will include descriptive statistics as well as frequency counts for the number of doses or cycles received, the total dose actually administered as well as the total dose intended, and the dose intensity, which is calculated as percentage of total dose actually administrated divided by total dose intended during whole treatment period up to the last dose of study drug. Dose intensity by cycle will be summarized.

Duration of study treatment exposure in days will be calculated as: date of EOTV – first dose date + 1 for patients who have discontinued treatment; date of data cutoff - first dose date + 1 for patients whose treatment is ongoing.

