# 8.3 End of Treatment Visit/Follow-up

# 8.3.1 End of Treatment Visit: 28-Days (4 Weeks) After Last Dose of Study Drug or at the Time of Treatment Failure

It is recognized that certain patients (such as those experiencing progression of disease) may be cared for in facilities other than the participating investigational site, may proceed to receive other anti-leukemic therapy, and/or may elect not to return to the investigational site. Therefore, this visit is considered optional, but should be carried out whenever possible.

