## Informed consent must be obtained prior to performing any screening procedures, and may be obtained prior to the start of the 14 day screening period.

			Screenin	g			Cycle 1 28 days	- 			Sub	sequent Cyc 28 days	cles		End of Treatment	
	Day	Up to -14 Days	Up to -5 Days	Up to -1 Days	1	8	15	22	25 and/or 26	1	8	15	22	25 and/or 26	28-days Following Last Treatment or At Time of Treatment Failure	Post- treatment Follow-up
	Study Day Window				+/- 1	+/- 1	+/- 1	+/- 1	+ 3	+/- 1	+/- 1	+/- 1	+/- 1	+ 3	+3	
	Week				1	2	3	4		5, 9, 13, etc.	6, 10, 14, etc.	7, 11, 15, etc.	8, 12, 16, etc.			
EVALUATIO	ON OR PROCEDURE															
STUDY DRU ADMINISTR	UG RATION															
TLS prophylaxis				Х												
Flotetuzumab 					$1 \rightarrow 7^{1}$	8→14 	15→21 	22→24 	25→28 	$1 \rightarrow 7^2$	8→14 	15→21 	22→24 	25→28 		
1. C W 2. Al 3. Al	
 
Cycle 1 only: flotetuzumab administration will occur Weeks 2-4: Dosing will follow the scheme shown in 2
 
All other cycles: flotetuzumab administration will oc
 
All cycles: Scheduled dose/bag changes have a ± 2 h
 
			ill occur fi own in Ta will occu e a ± 2 hou	rom Day 1ble 2 . 1r in a 7 . 1r windo	vs 1 to 28 -Day cont ow.	(7-day coi inuous inj	ntinuous I fusion sch	V infusion edule acco	). Week 1 c ording to T a	only: Patien a ble 2 .	ts will receiv	ve step-up d	osing as d	etailed in Table 2 .	
ELIGIBILIT	ſΥ															
Diagnostic Bone Marrow Aspirate and core biopsy for local histopathological and immunohistochemical analysis, central flow cytometric evaluation, and next generation sequencing		X 														
4. Ol	btain if not performed w	ithin 30 d	lays befor	e the star	t of treat	tment (Cy	cle I, Day	1) .								
Buccal mucosal sampling (Only Washington U., St. Louis, MO)																

			Screenin	g			Cycle 1 28 days	5			Sub	sequent Cy 28 days	cles		End of Treatment	
	Day	Up to -14 Days	Up to -5 Days	Up to -1 Days	1	8	15	22	25 and/or 26	1	8	15	22	25 and/or 26	28-days Following Last Treatment or At Time of Treatment Failure	Post- treatment Follow-up
	Study Day Window				+/- 1	+/- 1	+/- 1	+/- 1	+ 3	+/- 1	+/- 1	+/- 1	+/- 1	+ 3	+3	
	Week				1	2	3	4		5, 9, 13, etc.	6, 10, 14, etc.	7, 11, 15, etc.	8, 12, 16, etc.			
Medical hi	istory															
			х													

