12 SAFETY ANALYSES

12.1 Treatment Emergent Adverse Events

Only treatment-emergent AEs, defined as any event that is temporally associated with administration of study product, will be summarized in tables. Events prior to treatment (e.g., due to study-related procedure) will be listed in an appendix to the final study report. DLTs will be listed.

The following tables of AE data will be created to summarize the number and percent of patients who experience at least one event of each of the following types:

- All AEs
- Drug-related AEs
- AEs by CTCAE Grade
- Drug related AEs by CTCAE Grade
- AEs with CTCAE Grade severity \geq Grade 3
- Drug-related AEs with CTCAE Grade severity \geq Grade 3
- SAEs (this may be a listing if there are few events)
- Drug-related SAEs
- Fatal AEs (this may be a listing if there are few events)
- AEs that result in study discontinuation
- AEs that lead to withdrawal of study drug
- AEs categorized as AESI and/or IREs

Tabulated data will display the number and percent of patients that experience individual events by System Organ Class (SOC) and Preferred Term (PT). Events will be displayed alphabetically for SOC and in descending order of overall PT incidence within each SOC.

An overall summary of AEs will display the number and percent of patients who experience at least one event of each of the following types:

- Any AE
- Any drug-related AE
- Any AE with CTCAE Grade severity \geq Grade 3
- Any drug-related AE with CTCAE Grade severity \geq Grade 3
- Any SAE
- Any drug-related SAE

- Any AE that results in study or study drug discontinuation
- Any fatal AE
- Any AESI
- Any IREs

The following AESI will be summarized:

- All cytokine release syndrome or infusion related reaction events
- Grade 2 or greater immune-related AEs including, but not limited to, events of pneumonitis, colitis, autoimmune hepatitis, arthritis, glomerulonephritis, myocarditis and cardiomyopathy, hypophysitis, or thyroiditis
- Tumor lysis syndrome (TLS)
- Neutropenic sepsis/fungemia
- Grade 2 or greater neurological events.
- Capillary leak syndrome
- Epstein-Barr Virus (EBV) reactivation

The following summaries will be provided for AESI:

- All AESI
- Study drug related AESI
- Serious AESI
- Study drug related serious AESI
- AESI with CTCAE grade of Grade ≥ 3
- Study drug related AEs with CTCAE severity Grade ≥ 3

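### SAP 9 ends treatment exposure at the End of Treatment Visit instead of the last dose, overstating it by about 0 to 28 days; separately, the SAP 8.2.1 fallback age is always 1 or 2 years too high

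*SAP*

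**What the plan says.** **Exposure.** SAP 9 gives two rules for the duration of study treatment exposure. For patients off treatment it is "date of EOTV – first dose date + 1 for patients who have discontinued treatment"; for the others it is "date of data cutoff - first dose date + 1 for patients whose treatment is ongoing". The preceding paragraph of that section defines dose intensity with a different end point, using the "total dose intended during whole treatment period up to the last dose of study drug".

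The heading of Protocol 8.3.1 times the EOTV at "28-Days (4 Weeks) After Last Dose of Study Drug or at the Time of Treatment Failure", and the text says that "this visit is considered optional". The schedule of events in Protocol Appendix 1 repeats the timing ("28-days Following Last Treatment or At Time of Treatment Failure") and shows a +3-day window in that column.

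**Age.** SAP 8.2.1 says that either age or birth year is captured on the eCRF, and then: "Where age is not recorded, age will be calculated as follows: Age = year of informed consent- year of birth + 1".

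**The concern.** A duration of exposure should measure the span over which drug was given. The SAP rule runs on to a follow-up visit. Flotetuzumab is infused continuously, and Protocol 7.11.1 puts its elimination half-life at a few hours, so the days between last dose and visit cannot be counted as residual exposure.

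The tail is also not a constant that a reader could subtract. It is near zero when the visit is held at treatment failure close to the last dose, and four weeks when it is held on schedule. Its length therefore depends on why and when treatment ended. A patient who never attends the optional visit has no end date under this rule.

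The output is planned for both the safety and the efficacy population, and SAP 7.1 has efficacy-population summaries shown by PIF, ER and combined.

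The age formula is a separate matter. Where it is used, it feeds the demographic tables (SAP 8.2.1) and the under-70 versus 70-and-over subgroups for CR/CRh, CR, CRh and overall complete response (SAP 11.2.2).

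**Working it through.** The documents state no numerical result for either formula, so there is no figure to reproduce. The check is date arithmetic.

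**Exposure: inputs**
- SAP 9: end date is the EOTV for discontinued patients.
- Protocol 8.3.1 and Appendix 1: the gap *g* from last dose to EOTV is 28 days on schedule, 31 at the end of the +3-day window, and can be 0 if treatment failure is established on the last dosing day.
- Protocol 4.1: 28-day cycles of continuous infusion, at most 8 in total.

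**Exposure: formula**
- First to last dose: T = last dose − first dose + 1 = 28 × number of full cycles.
- SAP 9: (last dose + g) − first dose + 1 = T + g.
- Excess = g days; relative excess = g / T.

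| Full cycles | T (days) | SAP, g = 0 | SAP, g = 28 | SAP, g = 31 |
|---|---|---|---|---|
| 1 | 28 | 28 | 56 (+100%) | 59 (+110.7%) |
| 2 | 56 | 56 | 84 (+50%) | 87 (+55.4%) |
| 3 | 84 | 84 | 112 (+33.3%) | 115 (+36.9%) |
| 8 | 224 | 224 | 252 (+12.5%) | 255 (+13.8%) |

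Two patients who each received exactly one full cycle can thus be reported with 28 and 56 days of exposure. The relative error is largest for short treatment. Short treatment is foreseeable: Protocol 5.4 lists failure to reach at least PR after 2 cycles as a reason for withdrawal.

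**Age: formula.** Let D = consent year − birth year. Completed age at consent, A, is D if the birthday has been reached by the consent date and D − 1 if not. The SAP value is D + 1.
- Birthday reached: D + 1 − D = +1 year.
- Birthday not reached: D + 1 − (D − 1) = +2 years.

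The formula is never correct. Over all 365 × 365 pairs of consent and birth dates in one pair of years, the error is +1 in 50.1% and +2 in 49.9%.

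**Age: effect at the cut of 70**

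| Completed age | SAP value | Placed in 70 and over (SAP) | Value without the +1 | Placed in 70 and over (without +1) |
|---|---|---|---|---|
| 67 | 68 or 69 | none | 67 or 68 | none |
| 68 | 69 or 70 | about half | 68 or 69 | none |
| 69 | 70 or 71 | all | 69 or 70 | about half |

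The halves assume that birthdays and consent dates are spread evenly over the year.

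**The case against.** The text and the arithmetic are not in dispute. The case against concerns weight and remedy.

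- *Other exposure measures limit the harm.* SAP 9 also reports doses or cycles received, total dose given and intended, and dose intensity. A reader can see how much drug was received without using the duration. This is true, but those summaries do not correct the duration itself, which remains a planned output under the wrong name.
- *It may be an on-study period with a poor label.* SAP 8.3 uses the EOTV to bound concomitant medication, and AEs are collected to 28 days after the last dose. That may explain the choice of date. The SAP nevertheless calls the quantity treatment exposure.
- *The replacement is not pure time on drug either.* First to last dose still spans dosing interruptions, which Protocol 6.3 anticipates. It also spans the scheduled off-days of earlier patients on the 4-days-on, 3-days-off schedule, who belong to the safety population. This stands and should be disclosed. The replacement removes the post-treatment tail and gives an ordinary treatment duration, not infusion time.
- *The missing-visit gap may be closed elsewhere.* SAP 7.2 sends imputation of partial dates to the Statistical Programming Plan, which was not available for review. A visit that never took place is not a partial date, but the plan might cover it. That part stays open.
- *The percentages are illustrative.* They assume complete, uninterrupted cycles and the stated visit timing, and a late visit could exceed 31 days. That is correct.
- *The age formula may apply to nobody.* Correct; the number of patients without a recorded age is not given. The SAP provides for the case, however, and the formula is wrong whenever it is used.

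**Conclusion.** Both points hold and should be corrected.

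For discontinued patients, exposure as written exceeds the first-to-last-dose span by the gap to the EOTV: about 0 to 28 days by the planned timing, or 31 with the visit window. The mix of visit timings is not given, so no average overstatement can be claimed. Patients still on treatment at the data cutoff are unaffected.

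The fallback age is 1 or 2 years too high for every patient to whom it is applied. That group is limited to patients without a recorded age and could be empty.

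The consequences are confined to descriptive outputs: the exposure summaries, the age summaries and the age subgroups. The primary CR/CRh test, its boundaries, alpha and power do not use either quantity. The planned AE tables also stand, because they "summarize the number and percent of patients who experience at least one event" and use no exposure-time denominator.

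**What to change.** **SAP 9.** For discontinued patients, define duration of exposure as last dose date − first dose date + 1. Keep the data cutoff rule for patients still on treatment. State that the duration includes interruptions and scheduled off-days. This also aligns the section with its own dose-intensity period and removes the dependence on an optional visit.

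**SAP 8.2.1.** Define the fallback age as year of consent − year of birth, without the +1. State that a year-only derivation can still be up to one year too high, so about half of true 69-year-olds with a derived age would remain in the 70-and-over group.

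**Cost.** Two formula edits and a sentence of explanation for each. No new data are needed, because dose intensity already requires the last dose date. Reported exposure will be shorter wherever the visit falls after the last dose. The age error falls from 1–2 years to 0–1 year but does not disappear.
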